#### **5.3.3. Imputation rules for date of last contact and efficacy assessments**

##### **5.3.3.1. Date of last contact**

The date of last contact will be derived for patients not known to have died at the analysis cut-off using the latest complete date among the following:

- All patient assessment dates (blood draws (laboratory, PK), vital signs, performance status, ECG, tumor assessments)
- Start and end dates of anti-cancer therapies administered after study treatment discontinuation
- AE start and end dates
- Last date of contact collected on the 'Survival Follow-up' eCRF (do not use date of survival follow-up assessment unless status is 'alive')
- Study drug start and end dates
- Randomization date

- Withdrawal of consent date
- Date of discontinuation on disposition eCRF pages (do not use if reason for discontinuation is lost to follow-up).

Only dates associated with actual examinations of the patient will be used in the derivation. Dates associated with a technical operation unrelated to patient status such as the date a blood sample was processed will not be used. Assessment dates after the cut-off date will not be applied to derive the last contact date.

### **5.3.3.2. Death date**

Missing or partial death dates will be imputed based on the last contact date:

- If the date is missing it will be imputed as the day after the date of last contact
- If the day or both day and month is missing, death will be imputed to the maximum of the full (non-imputed) day after the date of last contact and the following:
  - Missing day: 1st day of the month and year of death
  - Missing day and month: January 1st of the year of death

### **5.3.3.3. Tumor assessments**

All investigation dates (eg, X-ray, CT scan) must be completed with day, month and year.

If there are multiple scan dates associated with an evaluation, ie, radiological assessments occur over a series of days rather than the same day, the choice of date of assessment could impact the date of progression and/or date of response. If there are multiple scan dates associated with an evaluation, the earliest of the scan dates associated with the evaluation will be used as the date of assessment.

If one or more investigation dates for an evaluation are incomplete but other investigation dates are available, the incomplete date(s) are not considered for calculation of the assessment date and assessment date is calculated as the earliest of all investigation dates (eg, X-ray, CT-scan).

If all measurement dates for an evaluation have no day recorded, the 1st of the month is used.

If the month is not completed, for any of the investigations for an evaluation, the respective assessment will be considered to be at the date which is exactly between the previous and the following assessment. If both a previous and following assessments are not available, this assessment will not be used for any calculations.

### **5.3.3.4. Date of start of new anti-cancer therapy**

Incomplete dates for start date of new anti-cancer therapy (drug therapy, radiation, surgery) will be imputed as follows and will be used for determining censoring dates for efficacy analyses and in the derivation of the end of on-treatment period. PD date below refers to PD date by investigator assessment.

- The end date of new anti-cancer therapy will be included in the imputations for start date of new anti-cancer therapy. If the end date of new anti-cancer therapy is
  - completely missing then it will be ignored in the imputations below
  - partially missing with only year (YYYY) available then the imputations below will consider 31DECYYYY as the end date of the new anti-cancer therapy
  - partially missing with only month and year available then the imputations below will consider the last day of the month for MMMYYYY as the end date of the new anti-cancer therapy
- For patients who have not discontinued study treatment at the analysis cut-off date, last dose of study treatment is set to the analysis cut-off date in the imputations below.
- If the start date of new anti-cancer therapy is completely or partially missing, then the imputed start date of new anti-cancer therapy is derived as follows:
  - Start date of new anti-cancer therapy is completely missing  
Imputed start date = min [max(PD date + 1, last dose of study treatment + 1), end date of new anti-cancer therapy]
  - Only year (YYYY) for start of anti-cancer therapy is available  
IF YYYY < Year of min [max(PD date + 1, last dose of study treatment + 1), end date of new anti-cancer therapy] THEN imputed start date = 31DECYYYY;  
ELSE IF YYYY = Year of min [max(PD date + 1, last dose of study treatment + 1), end date of new anti-cancer therapy]  
THEN imputed start date = min [max(PD date + 1, last dose of study treatment + 1), end date of new anti-cancer therapy]  
ELSE IF YYYY > Year of min [max(PD date + 1, last dose of study treatment + 1), end date of new anti-cancer therapy]  
THEN imputed start date = 01JANYYYY
  - Both Year (YYYY) and Month (MMM) for start of anti-cancer therapy are available  
IF  
    YYYY = Year of min [max(PD date + 1, last dose of study treatment + 1), end date of new anti-cancer therapy], AND  
    MMM < Month of min [max(PD date + 1 day, last dose of study treatment + 1 day), end date of new anti-cancer therapy]  
THEN  
    imputed start date = DAY (Last day of MMM) MMM YYYY;  
ELSE IF  
    YYYY = Year of min [max(PD date + 1, last dose of study treatment + 1), end date of new anti-cancer therapy], AND

```
MMM = Month of min [max(PD date + 1 day, last dose of study treatment + 1
day), end date of new anti-cancer therapy]
THEN
    imputed start date = min [max(PD date + 1 day, last dose of study treatment + 1
day), end date of new anti-cancer therapy]);
ELSE IF
    YYYY = Year of min [max(PD date + 1, last dose of study treatment + 1), end
date of new anti-cancer therapy], AND
    MMM > Month of min [max(PD date + 1 day, last dose of study treatment + 1
day), end date of new anti-cancer therapy]
THEN
    imputed start date = 01 MMM YYYY;
ELSE IF
    YYYY < Year of min [max(PD date + 1, last dose of study treatment + 1), end
date of new anti-cancer therapy]
THEN
    imputed start date = DAY (Last day of MMM) MMM YYYY;
ELSE IF
    YYYY > Year of min [max(PD date + 1, last dose of study treatment + 1), end
date of new anti-cancer therapy]
THEN
    imputed start date = 01 MMM YYYY.
```

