### **5.2.6. Definition of start of new anti-cancer therapy**

Start date of new anti-cancer therapy (drug, radiation, surgery) is used for censoring in efficacy analyses (see Section 6.1.2 and Section 6.2.2).

The start date of new anti-cancer therapy is the earliest date after the ‘start date’ amongst the following:

- Start date of anti-cancer drug therapy recorded in the ‘Follow-up Cancer Therapy’ eCRF pages
- Start date of radiation therapy recorded in ‘Concomitant Radiation Therapy’, and ‘Follow-up Radiation Therapy’ eCRF pages with ‘Treatment Intent’ = ‘Curative in intent’
- Surgery date recorded in ‘Concomitant Surgery’, and ‘Follow-up Surgery’ eCRF pages when ‘Surgery Outcome’ = ‘Resected’ or ‘Partially Resected’.

When start date of anti-cancer therapy is missing or partially missing, the imputation rules described in Section 5.3.3.4 should be applied using ‘Follow-up Cancer Therapy’, ‘Concomitant Radiation Therapy’, ‘Follow-up Radiation Therapy’, ‘Concomitant Surgery’, and ‘Follow-up Surgery’ eCRF pages.

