#### Combinations B, C and D

The following analyses will be based on the FAS by treatment group using the data from Phase 2 Cohorts for each combination.

Assessment of response will be made as per investigator using RECIST v1.1.

**Best overall response (BOR)** will be assessed based on reported overall lesion responses at different evaluation time points from the ‘start date’ until the first documentation of PD, according to the following rules. Only tumor assessments performed on or before the start date of any further anti-cancer therapies will be considered in the assessment of BOR. Clinical deterioration will not be considered as documentation of disease progression.

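### Surgery or curative radiotherapy on a 'Concomitant' page, with a missing or year-only date and no early end date, can be imputed months late, so scans after the procedure stay in the response assessment

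*SAP*

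**What the plan says.** Section 5.2.6 defines the start of new anti-cancer therapy used for censoring in the efficacy analyses. Besides follow-up drug therapy, it includes "Start date of radiation therapy recorded in ‘Concomitant Radiation Therapy’, and ‘Follow-up Radiation Therapy’ eCRF pages with ‘Treatment Intent’ = ‘Curative in intent" and "Surgery date recorded in ‘Concomitant Surgery’, and ‘Follow-up Surgery’ eCRF pages when ‘Surgery Outcome’ = ‘Resected’ or ‘Partially Resected". For incomplete dates from any of these pages, it says "the imputation rules described in Section 5.3.3.4 should be applied using" all five page types.

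Section 5.3.3.4 has one rule for all of them: "Incomplete dates for start date of new anti-cancer therapy (drug therapy, radiation, surgery) will be imputed as follows". With nothing recorded, "Imputed start date = min [max(PD date + 1, last dose of study treatment + 1), end date of new anti-cancer therapy". Call this the reference date.

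- Year only: the reference date if the years match, otherwise 31 December of an earlier year.
- Month and year: the last day of an earlier month, or the reference date if the month is the same.
- Therapy end date: the only cap. If "completely missing then it will be ignored in the imputations below".
- Still on treatment: "For patients who have not discontinued study treatment at the analysis cut-off date, last dose of study treatment is set to the analysis cut-off date".

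Section 6.1.2.1 then states: "Only tumor assessments performed on or before the start date of any further anti-cancer therapies will be considered in the assessment of BOR". The same start date governs maximum shrinkage (Section 6.2.2.1) and censoring for DR and PFS (Tables 9 and 11).

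**The concern.** The reference date presumes that the new therapy followed both progression and the end of study treatment. That is natural for the 'Follow-up' pages, and Section 6.5.5 uses only those pages to tabulate therapy after discontinuation. The 'Concomitant' pages therefore appear to hold procedures done while the patient was on study treatment, where the anchor points the wrong way. Surgery is described by a single date, so there is usually no end date to pull the imputation back.

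The stake is the primary endpoint. A date imputed too late leaves scans taken after a resection or curative irradiation inside the window for BOR. Section 6.1.2.1 also makes a patient a non-responder if other therapy came before CR or PR, but that safeguard depends on when the therapy is dated. ORR in Cohorts A1-A5 is tested against a fixed rate with no control group, so an error towards response is not offset elsewhere. The SAP's rules for incomplete AE and medication start dates (Sections 5.3.2.2 and 5.3.2.3) go the other way, to treatment start or the first of the period.

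**Working it through.** **1. Plan's own figures (Sections 5.1.1 and 5.1.2).** Exact binomial:
- A1-A4: P(X ≥ 8 | 28, 0.15) = 0.0486; power at 0.35 = 0.818.
- A5: P(X ≥ 12 | 35, 0.20) = 0.0344; power at 0.40 = 0.805.

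Both agree with the stated one-sided 0.05 and at least 80% power.

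**2. One worked patient (dates assumed).** 'Start date' 9 Jan 2017, surgery 20 Feb, PD 18 Sep, last dose 2 Oct 2017, no end date. Scheduled 8-weekly scans: 6 Mar, 1 May, 26 Jun, 21 Aug.
- Surgery date missing, or '2017' only: max(18 Sep + 1, 2 Oct + 1) = 3 Oct 2017. This is 225 days late and after both PD and last dose. All four post-surgery scans enter BOR. They are 8 weeks apart, so the 4-week confirmation requirement can be met. PD is a PFS event at (252 + 1)/30.4375 = 8.3 months.
- 'Feb 2017': imputed to 28 Feb, 8 days late. No post-surgery scan enters BOR.
- True date: no post-baseline scan precedes the surgery, so PFS is censored on the 'start date'.

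**3. The rule applied literally to simulated patients.** 50,000 per row. Assumed timings: last dose 60-499 days after start, procedure between day 14 and last dose, PD 10-399 days after the procedure, scans every 56 days throughout.

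| End date | Recorded start | Mean delay (days) | Max delay (days) | After both PD and last dose | PD treated as event | ≥2 post-procedure scans in BOR window before PD |
|---|---|---|---|---|---|---|
| None | Missing | 239 | 484 | 100% | 100% | 81% |
| None | Year only | 147 | 364 | 35% | 44% | 62% |
| None | Month and year | 15 | 30 | 0.2% | 1.7% | 0% |
| 7-44 days after start | Missing | 25 | 44 | 0.7% | 4.0% | 0% |
| 7-44 days after start | Year only | 24 | 44 | 0.6% | 3.7% | 0% |
| 7-44 days after start | Month and year | 13 | 30 | 0.1% | 1.2% | 0% |

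The percentages and mean delays depend on the assumed timings. The late direction does not, provided the procedure fell during study treatment: every branch that can then apply gives the latest date the record and the reference date allow. No simulated date was early.

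**4. Cost of one false responder.** If a cohort gained one with certainty, the effective bar drops by one:
- A1-A4: P(X ≥ 7 | 28, 0.15) = 0.1152.
- A5: P(X ≥ 11 | 35, 0.20) = 0.0747.

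If it happened with probability q (not given in the SAP), the A1-A4 error is 0.0486 + (0.1152 − 0.0486)q = 0.0486 + 0.0666q. This gives 0.0493 at q = 1% and 0.0519 at q = 5%.

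**The case against.** **A broader reading does not stand.** A reader might infer that any incompletely dated local therapy turns its shrinkage into drug response and leaves the patient uncensored. The SAP does not support that. With the month known the delay is at most about 30 days, too short for two 8-weekly scans, although one late scan could still confirm an earlier PR. A recorded radiotherapy end date caps the imputation. Patients without PD are still censored, only later than they should be.

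**Timing is inferred.** The SAP does not define the window of the 'Concomitant' surgery and radiation pages. For medications (Section 6.5.4), concomitant use extends through the on-treatment period, which can run to 30 days after last dose (Section 5.2.7). It would go too far to say the imputed date is one on which the procedure could not have happened. Section 6.5.5 favours the on-treatment reading but does not settle it.

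**A false PR needs further steps.** The investigator reports response per RECIST v1.1 and NE is available, so a resected target lesion would have to be reported as a response twice. The protocol may also restrict such procedures. These points lower the likelihood; nothing in the SAP corrects the date.

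**Frequency.** Section 2 specifies cleaned eCRF data, so an on-study resection without even a month should be rare. The analysis follows last subject last visit, so the cut-off substitution for ongoing patients should seldom apply. Both points stand.

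**An extreme early date is not neutral.** Placing every completely missing date just after the 'start date' would discard genuine responses and observed PFS or DR events. That is right, and it shapes the fix.

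**Conclusion.** The defect is real but narrow. It bites when a 'Concomitant' procedure has a completely missing or year-only date and no early end date: mainly surgery, or radiotherapy without an end date. The start can then be months late, to as far as after both PD and last dose. Post-procedure scans stay in BOR and a later PD becomes a PFS or DR event. For ORR any error runs towards response; for PFS and DR the departure from the SAP's own censoring rule is clear, but no direction of bias is shown.

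The conclusion assumes that the 'Concomitant' pages record therapy given during study treatment. The number of patients is unknown and probably small. One false responder could still reverse a declaration, at 7/28 versus 8/28 or 11/35 versus 12/35. A reader might take 0.115 and 0.075 as the tests' actual error rates. They are upper bounds for a single false responder occurring with certainty, and no figure in the SAP supports that frequency. The point merits correction because the rule is wrong for these pages and cheap to change.

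**What to change.** In Section 5.3.3.4, limit the max(PD + 1, last dose + 1) anchor to the 'Follow-up' pages. For 'Concomitant Surgery' and 'Concomitant Radiation Therapy':

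- **Partial date:** use the earliest date after the 'start date' compatible with the recorded parts. A missing day becomes the 1st of the month; a missing day and month becomes 1 January. If the result is on or before the 'start date', use the following day. Never go later than a recorded end date.
- **Completely missing date:** in the primary ORR, do not count the patient as a responder on scans that cannot be shown to precede the procedure. Report ORR, PFS and DR under both the earliest and the latest compatible date; do not make Day 1 censoring of PFS the only analysis.

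In the worked patient, the partial-date rule gives 10 Jan 2017 (year only) or 1 Feb 2017 (month known). No post-surgery scan then enters BOR, and PFS is censored before PD.

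The cost is a few lines of SAP text, one programming branch by eCRF page and a small sensitivity table. Section 5.2.5 already restricts imputation by page for the on-treatment period. The downside is that a few incompletely dated patients may lose a response or be censored earlier.

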## 6. ANALYSES AND SUMMARIES

Refer to Section 4 for definitions of analysis sets and Section 5.2 for general methodology.

### 6.1. Primary Endpoints

#### 6.1.1. DLT for Phase 1b lead-in

##### 6.1.1.1. Primary analysis

The following analyses will be based on the DLT-evaluable set for patients in the Phase 1b for all combinations. DLTs will be listed and summarized by treatment group for Phase 1b cohorts.

## 6.1.2. Confirmed OR as assessed by the Investigator per RECIST v1.1 for Phase 2

### 6.1.2.1. Primary analysis

#### Combinations A and F

The following analyses will be based on the FAS by treatment group using the data from the combined Phases 1b and 2 (Cohorts A1, A2, A3 and Cohorts F1, F2, F3) and the data from Phase 2 (Cohorts A4, A5, A6, A7, A8, A9, A10).

#### Combinations B, C and D

The following analyses will be based on the FAS by treatment group using the data from Phase 2 Cohorts for each combination.

Assessment of response will be made as per investigator using RECIST v1.1.

**Best overall response (BOR)** will be assessed based on reported overall lesion responses at different evaluation time points from the ‘start date’ until the first documentation of PD, according to the following rules. Only tumor assessments performed on or before the start date of any further anti-cancer therapies will be considered in the assessment of BOR. Clinical deterioration will not be considered as documentation of disease progression.

#### **BOR Based on Confirmed Responses:**

- CR = at least two determinations of CR at least 4 weeks apart and before first documentation of PD
- PR = at least two determinations of PR or better (PR followed by PR or PR followed by CR) at least 4 weeks apart and before first documentation of PD (and not qualifying for a CR)
- SD (applicable only to patients with measurable disease at baseline) = at least one SD assessment (or better)  $\geq 6$  weeks after the ‘start date’ and before first documentation of PD (and not qualifying for CR or PR)
- Non-CR/non-PD (applicable only to patients with non-measurable disease at baseline) = at least one non-CR/non-PD assessment (or better)  $\geq 6$  weeks after the ‘start date’ and before first documentation of PD (and not qualifying for CR or PR).
- PD = first documentation of PD  $\leq 12$  weeks after the ‘start date’ (and not qualifying for CR, PR, SD or non-CR/non-PD)
- NE: all other cases.

An objective status of PR or SD cannot follow one of CR. SD can follow PR only in the rare case that tumor increases by less than 20% from the nadir, but enough that a previously documented 30% decrease from baseline no longer holds. If this occurs, the sequence PR-SD-PR is considered a confirmed PR. A sequence of PR – SD – SD – PD would be a best response of SD if the window for SD definition has been met.

**Objective Response (OR)** is defined as confirmed BOR of CR or PR according to RECIST v1.1.

Patients who do not have a post-baseline radiographic tumor assessment due to early progression, who receive anti-cancer therapies other than the study treatments prior to reaching a CR or PR, or who die, progress, or drop out for any reason prior to reaching a CR or PR will be counted as non-responders in the assessment of OR. Each patient will have an objective response status (0: no OR; 1: OR). OR rate (ORR) is the proportion of patients with OR in the analysis set.

A formal test of hypothesis for each treatment group (Cohorts A1, A2, A3, A4, and A5 only) in Combination A will be performed at the 1-sided significance level  $\alpha=0.05$  based on the exact binomial test as described in Section 5.1.1.

ORR by treatment group will also be calculated along with the 2-sided 90% CI using the Clopper-Pearson method (exact CI for a binomial proportion as computed by default by the FREQ procedure using the EXACT option). Two-sided 95% CIs will also be calculated and reported.

In addition, the frequency (number and percentage) of patients with a confirmed BOR of CR, PR, SD, non-CR/non-PD (applicable only to patients with non-measurable disease at baseline), PD, and NE will be tabulated. Patients with confirmed BOR of NE will be summarized by reason for having NE status. The following reasons will be used:

- No baseline assessment
- No post-baseline assessments due to death
- No post-baseline assessments due to other reasons
- All post-baseline assessments have overall response NE
- New anti-cancer therapy started before first post-baseline assessment
- SD of insufficient duration (<6 weeks after the 'start date' without further evaluable tumor assessments)
- PD too late (>12 weeks after the 'start date')

Special and rare cases where BOR is NE due to both SD of insufficient duration and late PD will be classified as 'SD of early' (ie, SD of insufficient duration).

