#### 6.2.2.5. Progression-free survival

Progression-Free Survival (PFS) is defined as the time from the ‘start date’ to the date of the first documentation of PD or death due to any cause, whichever occurs first.

PFS data will be censored on the date of the last adequate tumor assessment for patients who do not have an event (PD or death), for patients who start a new anti-cancer therapy prior to an event (see Section 5.2.6) or for patients with an event after 2 or more missing tumor assessments. Patients who do not have an adequate baseline tumor assessment or who do not have an adequate post-baseline tumor assessment will be censored on the ‘start date’ unless death occurred on or before the time of the second planned tumor assessment (ie ≤ 16 weeks after the ‘start date’) in which case the death will be considered an event.

In this study antitumor activity will be assessed through radiological tumor assessments conducted at screening and every 8 weeks (±7 days) until PD regardless of initiation of subsequent anti-cancer therapy. After 1 year from the ‘start date’, tumor assessments will be

conducted at 12-week ( $\pm 7$  days) intervals and after 2 years from the ‘start date’, tumor assessments will be conducted at 16-week ( $\pm 7$  days) intervals.

The censoring and event date options to be considered for the PFS and DR analysis are presented in Table 11.

$$\text{PFS (months)} = [\text{date of event or censoring} - \text{‘start date’} + 1] / 30.4375$$

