**Table 11. Outcome and Event Dates for PFS Analyses**

Scenario	Date of event/censoring	Outcome
No adequate baseline assessment	‘Start date’ a	Censored a
PD or death - After at most one missing or inadequate post-baseline tumor assessment, OR - $\leq 16$ weeks after the ‘start date’	Date of PD or death	Event
PD or death - After 2 or more missing or inadequate post-baseline tumor assessments	Date of last adequate tumor assessment b documenting no PD before new anti-cancer therapy is given or missed tumor assessments	Censored
No PD and no death	Date of last adequate tumor assessment b documenting no PD before new anti-cancer therapy is given or missed tumor assessments	Censored
Treatment discontinuation due to ‘Disease progression’ without documented progression	Not applicable	Information is ignored. Outcome is derived based on documented progression only.
New anti-cancer therapy given	Date of last adequate tumor assessment b documenting no PD before new anti-cancer therapy is given or missed tumor assessments	Censored

a However if the patient dies  $\leq 16$  weeks after the ‘start date’ the death is an event with date on death date

b If there are no adequate post-baseline assessments prior to PD or death, then the time without adequate assessment should be measured from the ‘start date’; if the criteria were met the censoring will be on the ‘start date’

Kaplan-Meier estimates (product-limit estimates) will be presented by treatment group together with a summary of associated statistics including the median PFS time with 2-sided 95% CIs. In particular, the PFS rate at 2, 4, 6, 8, 10, 12 and 18 months will be estimated with corresponding 2-sided 95% CIs. The CIs for the median will be calculated according to Brookmeyer and Crowley (1982) and the CIs for the survival function estimates at the time points defined above will be derived using the log-log transformation according to Kalbfleisch and Prentice (2002) (conftype=loglog default option in SAS Proc LIFETEST) with back transformation to a CI on the untransformed scale. The estimate of the standard error will be computed using Greenwood’s formula.

Frequency (number and percentage) of patients with each event type (PD or death) and censoring reasons will be presented by treatment group. Reasons for censoring will be summarized according to the categories in Table 12 following the hierarchy shown.

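### The 12-week limit for a best response of PD falls between the first and second planned scans, so some progression that counts as a PFS event is tabulated as not evaluable (descriptive table only, low priority)

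*SAP*

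**What the plan says.** All references are to the SAP.

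- **BOR, Section 6.1.2.1.** The PD category is "PD = first documentation of PD" no later than 12 weeks after the 'start date', for a patient who does not qualify for CR, PR, SD or non-CR/non-PD. The last category is "NE: all other cases".
- **Reasons for NE, Section 6.1.2.1.** One listed reason is "PD too late (>12 weeks after the" start date). A different one, "All post-baseline assessments have overall response NE", cannot apply once a scan has shown PD.
- **Scan schedule, Section 6.2.2.5.** In the first year tumors are assessed "every 8 weeks (±7 days) until PD". The same section treats 16 weeks as the second planned assessment: a death "on or before the time of the second planned tumor assessment" is an event even for a patient without an adequate baseline or post-baseline assessment.
- **PFS events, Table 11.** PD or death is an event on its own date if it comes "After at most one missing or inadequate post-baseline tumor assessment, OR" if it comes within 16 weeks of the 'start date'. Censoring for missed scans needs two or more missing or inadequate assessments. Under Section 5.2.11 an NE scan is not an adequate one.

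The SAP gives no reason for 12 weeks and does not tie it to the scan schedule.

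**The concern.** A time limit on BOR of PD normally serves to exclude progression found only after a long unobserved gap. To do that sensibly it should match a planned scan. The PFS limit does, at the second planned scan. The BOR limit matches none: it falls in the interval between the first and second scans. Among planned scans done on time, only the first can give a BOR of PD.

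The patient affected has a missed or NE first scan and PD at the scheduled second scan. The PFS rules tolerate that single gap; the BOR rule does not. The BOR table then shows a patient with radiologically documented progression as not evaluable. A reader comparing the BOR table with the PFS event counts will find PD events among NE patients, and the SAP does not explain why.

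**Working it through.** **Inputs.** Scan interval 8 weeks ±7 days and second planned assessment at 16 weeks (Section 6.2.2.5); BOR limit 12 weeks (Section 6.1.2.1); PFS event rule (Table 11); cohort sizes 20, 25, 28 and 35 (Section 5.1.1).

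**The plan's own figure.** Second planned scan = 2 × 8 = 16 weeks = day 112. This reproduces the 16 weeks in Section 6.2.2.5.

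**Scan windows**, in days after the 'start date', as 56k ± 7:

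- Scan 1: 56 ± 7 = days 49–63 (weeks 7–9)
- Scan 2: 112 ± 7 = days 105–119 (weeks 15–17)
- BOR limit: 12 × 7 = day 84, which is 21 days after scan 1 closes (84 − 63) and 21 days before scan 2 opens (105 − 84)

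**The two rules applied to the same patient.** Assume an adequate baseline, measurable disease and no new anti-cancer therapy before PD.

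| Scans | BOR as written | PFS (Table 11) | BOR with a 17-week limit |
|---|---|---|---|
| PD at week 8 | PD | Event | PD |
| Late or unscheduled scan, PD at week 12 | PD | Event | PD |
| Week 8 missed or NE, PD at week 16 | NE (late PD) | Event | PD |
| Week 8 missed or NE, PD at week 17 | NE (late PD) | Event, only by the one-missing limb | PD |
| Week 8 SD, PD at week 16 | SD | Event | SD |
| Weeks 8 and 16 missed, PD at week 24 | NE (late PD) | Censored | NE (late PD) |

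The rules diverge in rows 3 and 4 only. With two missed scans (last row) they agree that the progression is too remote to use. A limit of exactly 16 weeks would mend row 3 but leave days 113–119 as late PD, although a scan on those days is on schedule.

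**Size per patient.** One patient moved from NE to PD is 1/20 = 5.0%, 1/25 = 4.0%, 1/28 = 3.6% or 1/35 = 2.9% of the cohort.

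**What does not move.**

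- Section 6.1.2.1 counts the patient as a non-responder under either label, so ORR and its interval are fixed.
- Neither PD nor NE is disease control (Section 6.2.2.2), so DCR is fixed.
- The decision rules in Section 5.1.2 depend on responder counts alone. At least 8 of 28 gives a one-sided alpha of 0.0486 and power of 0.818 (15% against 35%). At least 12 of 35 gives 0.0344 and 0.805 (20% against 40%). The PD/NE split enters neither.

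**The case against.** The case for leaving the rule alone has four parts.

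1. **Nothing inferential depends on it.** This stands. The BOR frequencies sit in the primary analysis section but are an added descriptive table. A reader might infer that the primary analysis is in error; the SAP does not support that.

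2. **The category is prespecified and visible.** Late PD is its own NE reason, so adding it to the PD row nearly recovers the total of documented PD without a better response. This stands too and limits the harm, but the PD and NE rows as printed remain out of line with the schedule.

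3. **Status at week 8 is unknown.** The patient might have had stable disease then, so NE is a cautious label, and BOR and PFS ask different questions. It is right that one cannot say such a patient never did better than PD; one can say only that no better response was documented. But this does not defend 12 weeks. Section 6.1.2.1 builds BOR from reported responses, and the rule already accepts a lone PD as late as week 12 with equally little known beforehand.

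4. **A 17-week limit does not align the rules fully.** The one-missing limb of Table 11 has no week limit, so PD on a second scan done late, say at week 18, could still be a PFS event and NE for BOR. This stands, and it is why the fix includes a footnote.

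A reader might also conclude that the 12-week rule can only ever capture the first scan. That goes too far: Section 5.2.9 brings unscheduled visits into the efficacy analyses, and a late or unscheduled scan by day 84 can give a BOR of PD.

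**Conclusion.** The mismatch is real and small. The 12-week limit does not fit an 8-weekly schedule. For one defined type of patient it labels as NE a progression that Table 11 accepts as an event: first scan missed or NE, no better response documented, adequate baseline, no intervening anti-cancer therapy, PD at the scheduled second scan. The effect is 2.9% to 5.0% of a cohort per such patient, in two rows of a descriptive table. These patients stay identifiable through the NE reason.

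The SAP does not allow their number to be derived. Purely as an illustration, suppose 5–15% of patients have a missed or NE first scan and 50–70% of those show PD at the second. Then 28 × 0.05 × 0.5 = 0.7 to 28 × 0.15 × 0.7 = 2.9 patients of 28 would move. Both ranges are assumptions without support in the SAP. The upper end may be generous, since some patients who miss the first scan will die, withdraw or start other therapy before the second. The conclusion does not rest on that range. Low priority.

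**What to change.** In Section 6.1.2.1, replace 12 weeks in both the PD definition and the NE reason with the second planned tumor assessment including its window: BOR of PD if first PD is no later than 17 weeks (day 119) after the 'start date', and late PD only beyond that. The 17 weeks is the SAP's own 16 weeks plus its own 7-day window. Add a table footnote that any remaining late-PD patient may still be a PFS event, because Table 11 accepts PD after at most one missing or inadequate assessment.

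The cost is two numbers and a footnote. The reported PD rate will rise slightly and NE will fall by the same count. No new data are needed, and ORR, its test and interval, DCR, PFS and the decision rules are untouched.
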